## 7.5.7 Radiology tests

A **gallbladder ultrasound** will be locally performed in the Screening Phase (this will be considered as baseline data), on Week 24 in the Main Phase, and Weeks 48 and 96 in the Extension Phase. Patients with history of symptomatic colelithiasis are excluded from participation in the study (refer to Section 5.2). Information on the presence and location of gallstones, gallbladder sediments, and bile dilation will be entered in the Gallbladder Ultrasound eCRF page. In case of abnormal liver function criteria (refer to Section 7.5.2.3), an abdominal ultrasound will be required (liver and bile duct).

#### **MRI Evaluation / Tumor volume measurement:**

Patients will undergo MRI evaluations in the Screening Phase (these will be considered as baseline data), and on Visits 4 (Week 4), 7 (Week 12), and 10 (Week 24). MRIs will be evaluated by a central reviewer. At least 4 MRIs are expected to be evaluated by central review during the Main Phase of the study. In the Extension Phase, MRI evaluations will be performed on Weeks 48, 72, and 96.

Coronal and sagittal images weighted at T1 will be obtained before and after administration of gadolinium contrast. The minimum scanner field power will be 1.5 T.

MRIs will be submitted for evaluation by a blinded central evaluator. In order to ensure consistency in all participating sites, MRIs must be performed and processed according to the guidelines of the central evaluator's facility, which will be distributed to the sites before study start. These pituitary adenomas will be measured for analysis by a neuro-radiologist, using manual tracing together with the imaging analysis software.

Total tumor volume will be derived from coronal image with gadolinium and estimated by multiplying each slice thickness by the area within the curve of the imaging with manual tracings and adding the slices' volumes. The largest diameter at any plan will determine the maximum diameter of the tumor.

A change  $\geq 20\%$  in the original volume of the tumor will be considered clinically significant. Smaller changes in pituitary tumor volumes may be attributed to volume measurement artifacts, changes in the position of the slice, or time of administration of the contrast bolus (Jimenez et al 2008)(Colao et al 2009).

# 7.5.8 Electrocardiogram (ECG)

All ECGs will be locally performed. An ECG will be performed in the Screening Period or Visit 1 (to evaluate eligibility) and then on all visits before injection of the study drug in the Main Phase, except for Visits 3 and 6, on which they will be performed independently of drug administration. In the Extension Phase, ECGs will be performed on Weeks 36, 48, 60, 72, 84, and 96.

It is recommended that paper speed be programmed to 25 mm/s, and sensitivity to 10 mm/mV (calibration). The operator must sign and date all tracings performed. The abnormalities seen must be recorded in the ECG eCRF.

If a clinically significant abnormality is detected, the ECG will be repeated, at the Investigator's discretion, until the abnormality is resolved. More frequent ECGs may be performed at the Investigator's discretion, if clinically indicated. Any abnormalities must be recorded in the unscheduled evaluation pages of the eCRF.

Data safety records must include the following:

- Any abnormal ECG findings (refer to Section 7.5.2.2)
- Abnormal vital signs
- All arrhythmias, including: Torsades de Pointes, ventricular tachycardia, ventricular fibrillation, and ventricular flutter
- Syncope, near-syncope, and fainting
- Seizures or loss of central function (sudden incontinence, dizziness, visual disorders)
- Sudden death

The study number must be recorded as [CSOM230D2401] at each tracing and must be kept in the source-documents.

#### 7.5.9 Visual evaluations

Visual field evaluations will be performed at screening, on Visit 2 (if the visual field evaluation at Screening is performed no more than 14 days before Visit 2, it may be considered as baseline data and there is no need to repeat it for Visit 2), on all visits in the Main Phase, except for Visit 3 and 6, and on Weeks 48, 72, and 96 in the Extension Phase. The window to perform the visual field evaluation must be of no more than 7 days before the scheduled visit.

Standard Automated Perimetry (SAP) is the most frequently used parameter to estimate the severity of visual loss (Monteiro et al 2009). The use of a Humphrey Field Analyzer is recommended.

#### **Visual Field Test**

The visual field test will be performed using SAP. The use of a Humphrey Field Analyzer is recommended. The perimeter software will use the refractive correction for near vision, calculated according to the patient's age (Monteiro et al 2009).

These test reports will determine whether the visual field is **normal or abnormal**. If abnormal, it will be classified as:

- **mild** (corrected visual acuity within normal limits (better than 20/30), in addition to nasal visual field within normal limits and impairment of approximately one quadrant of the temporal visual field) or
- **severe** (impaired corrected visual acuity (20/30 or worse), or impaired nasal visual field or impairment of more than one quadrant in the temporal visual field).

Outcome information will also be provided in the follow-up report: Stable, improved, or worsened visual field.

## 7.6 Tolerability

In addition to overall safety data, information on dose decreases will be collected. Furthermore, any AEs related to the study drug, e.g., gastrointestinal disorders, glucose metabolic disorders, cardiac dysfunctions, laboratory abnormalities, infections, and injection site reactions, will be summarized through the submission of counts and percentages for each treatment group.

## 7.7 Patient reported outcomes

Not applicable.

# 8 Safety monitoring

# 8.1 Serious adverse event reporting

In order to ensure patient safety, each SAE, **regardless of the suspected causality**, occurring after the beginning of any period in which the study protocol interferes with the standard medical care given to the patient (for example, withdrawal of treatment during washout period, change in treatment for a fixed dose of concurrent drug) and up to 56 days after the patient receives the last IM LAR injection of the study drug must be reported to Novartis within 24 hours after acknowledgement. Any SAE experienced after this period must be reported to Novartis if the investigator suspects that there is a causal relationship to the study drug. Recurrent episodes, complications, or progression of the initial SAE must be reported as a follow-up to the original episode within 24 hours of receipt of the follow-up information by the investigator. A SAE occurring in a different timepoint or considered as not otherwise related to a previously reported event, must be reported separately as a new event.

The information about all SAEs is collected and recorded in the Serious Adverse Event Report Form. The investigator must evaluate and register the relationship between each SAE and each specific study drug (if there is more than one study drug), complete the SAE Report Form in English, and fax it, completed and signed, within 24 hours to the Novartis Integrated Medical Safety (IMS) Oncology Department.

The site-specific phone and fax numbers of the contact people at the local IMS department are indicated in the investigator's binder provided to each site. The original copy of the SAE Report Form and the fax confirmation page must be kept together with the documentation of the case report form at the study site.

Follow-up information is submitted to the same person as the original SAE Report Form, using a new SAE Report Form, indicating that this is a follow-up of a previously reported SAE and mentioning the date of the original report. Each recurrence, complication, or progression of the original event must be reported as a follow-up to that event, regardless of when it occurs. Follow-up information must describe whether the event resolved or continues, whether and how it was treated, whether there was unblinding or not, and whether the patient continued or discontinued his/her participation in the study.

If the SAE is not previously documented in the Investigator's Brochure or the Package Insert (new occurrence), and if it is considered related to the Novartis study drug, an associate from Novartis IMS Oncology Department may request emergency additional information to the investigator for notification of the Health Authority. Novartis may need to issue an IN to inform all investigators involved in any study with the same medication reported for this SAE. Suspected Unexpected Serious Adverse Reactions (SUSARs) will be collected and reported to relevant authorities and ethics committees, according to Directive 2001/20/EC or according to the national regulatory requirements in the participating countries.

# 8.2 Pregnancy

In order to ensure patient safety, every pregnancy in a patient under administration of the study drug must be reported to Novartis within 24 hours from acknowledgement of its occurrence. Pregnancy must be followed up in order to determine the outcome, including miscarriage or abortion, details about the birth, and presence or absence of any birth defect, congenital anomalies, or maternal and/or newborn complications.

Pregnancy must be recorded in a Clinical Trial Pregnancy Form and reported by the investigator to the Local Novartis Integrated Medical Safety (IMS) Department. The pregnancy follow-up must be recorded in the same form and must include an evaluation of the possible relationship of any pregnancy outcome to the Novartis study drug. Any SAE experienced during pregnancy must be reported in the SAE Report Form.

Information about pregnancy of female partners of any men receiving the study drug during the study must be collected. The consent to report the information about this pregnancy must be obtained from the mother.

# 9 Data review and management

## 9.1 Site monitoring

Before the study is started, in a site initiation visit or in a meeting with the investigator, the Novartis team (or an appointed CRO) will review the protocol and eCRFs with the investigators and their staff. During the study, the field monitor will visit the site regularly to check for correct completion of patient records, accuracy of eCRFs records, compliance with the protocol and Good Clinical Practice (GCP), enrollment progress, and ensure that the study drug is stored, dispensed, and accounted for according to specifications. The main study staff must be available to assist the field monitor during these visits.

The investigator must keep the source-documents for each patient in the study, consisting of case and visit notes (hospital or clinic records) containing demographics and medical information, laboratory data, ECGs, and results of any other tests or evaluations. All information contained in the eCRFs must be traceable to these source-documents in the patient's file. The investigator must also keep the original informed consent form signed by the patient (a signed copy is given to the patient).

The investigator must facilitate the monitor's access to all relevant source-documents to confirm their consistency with the insertions in the eCRF. Novartis monitoring rules require complete verification for presence of the consent form, compliance with inclusion / exclusion criteria, documentation of SAEs, and recording of data that will be used for all primary and safety variables. Additional verifications regarding the consistency of the source-data with eCRFs are conducted according to the specific monitoring plan for the study. No information on the source-documents about the patients' identity will be disclosed.

## 9.2 Data collection (eCRF)

The investigator's designated staff must enter the information required by the protocol in the Novartis eCRFs. Field monitors will review the eCRFs for completion and accuracy and will instruct the site personnel to perform any corrections or inclusions required.

# 9.3 Database management and quality control

The data of eCRFs are entered in the study database by the CRO Data Management team after its own internal standard operating procedures are reviewed and approved by Novartis.

Then, the data entered are systematically verified by the CRO Data Management team with the use of error messages printed from validation programs and database listings. Obvious errors are corrected by the CRO Data Management personnel. Other errors or omissions are entered in electronically created Data Query Forms. The investigator (or his/her designee) will answer / resolve the query directly in the system. All changes are recorded in the study audit, which will capture who, when, and what files were corrected / changed. Quality control auditing of all main safety and efficacy data in the database is performed before database lock.

Concurrent medication entered in the database will be coded with the use of the WHO Drug Reference List, which uses the Anatomical Therapeutic Chemical (ATC) classification system. The medical history / current medical conditions and AEs will be coded with the use of the terminology of the Medical Dictionary for Regulatory Activities (MedDRA).

Laboratory samples, which will be centrally processed, will have their results submitted to the investigators.

ECG readings will be locally processed and the results will be entered in the eCRF.

The occurrence of any protocol breach will be determined. After the completion of these actions and after the database is declared complete and accurate, it will be locked and made available for data analysis. Any subsequent changes in the database may be performed only upon mutual written agreement between the Global Head of Biostatistics and Statistical Reporting and the Global Head of the Therapeutic Area.

# 10 Statistic methods and data analysis

The following sections describe the analyses to be performed.

For the Main Phase of the study, efficacy and safety analyses will be performed with the data collected when all patients enrolled complete their EOS visit. All Follow-up Visit safety data from patients who do not enter the Extension Study will also be included in the safety analyses of the Main Study. A final analysis will be performed when all Extension patients complete their last visit and will be reported either as an additional clinical study report or as an amendment to the Main Phase report. The other additional data at the end of the main study will be analyzed and summarized later in an additional clinical trial report or in a main study report.

Novartis or the designated CRO will analyze all data using the SAS System for data analysis V8.0 or higher. Any data analysis performed independently by an investigator must be submitted to Novartis before its publication or presentation.

Data from all participating sites in this study will be pooled so the appropriate number of patients is available for analysis. The statistical analysis methods described in this section will focus on the data analysis in the main study. Similar methods will be used in the analyses during the extension phase, as appropriate.

# 10.1 Analysis populations

Full analysis set (FAS): comprises all patients successfully completing Screening and receiving at least one dose of the study medication. The FAS will be the primary analysis set for efficacy analyses.

Page 86

**Safety analysis set:** comprises all patients receiving at least one dose of the study drug and having at least one post-baseline safety evaluation.

It is noteworthy that the statement that a patient did not experience AEs (in the Adverse Event eCRF) constitutes a safety evaluation. The safety set will be used for all safety analyses.

The analyses presented in these sections correspond to the analyses to be used for the Main Phase of the study. A final analysis will be performed when all Extension patients complete their last visit and will be reported either as an additional clinical study report or as an amendment to the Main Phase report.

# 10.2 Demographics / other baseline patient characteristics

Demographics and other baseline data, including disease characteristics (e.g., age, gender, and race), will be descriptively summarized based on the FAS. Categorical data will be presented as frequencies and percentages. For continuous data, the mean, standard deviation, median, minimum, and maximum will be presented.

## 10.3 Treatments (study drug, concurrent therapies, compliance)

Duration of exposure to the study drug, number of patients with dose adjustment (dose interruptions, changes), and dose intensity will be summarized for the main period and the study extension period.

Significant concurrent medication and non-drug therapies administered before and after the beginning of the administration of the study drug will be summarized by preferred terms, according to ATC class of the WHO Drug Reference List.

## 10.4 Primary objective

The primary objective is to evaluate the efficacy of pasireotide LAR on NFPA, based on tumor volume decrease.

#### 10.4.1 Variable

The primary efficacy variable is the proportion of patients with NFPA reaching a tumor volume decrease of at least 20% after treatment Week 24 with pasireotide LAR.

#### 10.4.2 Statistical analysis

The proportion of patients with a decrease of at least 20% in tumor volume will be summarized in terms of incidence rates and the exact 90% confidence interval at the end of the main study for the FAS population (week 24).

## 10.4.3 Control of missing values / censoring / discontinuations

A patient whose tumor volume evaluation at the beginning of the study (Screening Period, baseline data) is missing will not be considered for efficacy evaluations. Only patients with baseline evaluation and at least one later evaluation will be considered for statistical analysis. All analyses will be performed with the data observed, i.e. the primary analysis (Week 24) will only be based on data from patients with both baseline and Week 24 tumor volume evaluation.

The primary endpoint analyses will be based on the cases seen, as the population is treatmentnaïve (also not having undergone surgery), and 24 weeks of treatment are expected to be necessary before a significant effect is evaluated.

#### 10.4.4 Support Analysis

A sensitivity analysis will be performed in the primary efficacy endpoint after the imputation of missing values on week 24 from the last observation carried forward (LOCF). This will be possible for patients with baseline data and at least one later value.

# 10.5 Secondary objectives

#### **Analysis population**

All secondary efficacy analyses will be based on the full analysis set (FAS). The safety analysis set will be used for all safety analyses.

# 10.5.1 Efficacy variables and analysis

The secondary efficacy endpoints are described on section 3.3.2.

The changes in mean and percent tumor volume variation from baseline to Weeks 4, 12, and 24 will be presented together with the 90% confidence interval (90% CI). If the data are in a non-normal distribution, median CI will also be generated. The incidence rate of patients with tumor volume decrease  $\geq$  20% and its exact CI will be reported on weeks 4 and 12.

Summary of the statistical analyses will be provided for each disease-related symptom (headache, visual disorders, fatigue, decreased libido, and specific symptoms for men and women) on each visit. Changes in baseline scores will be summarized on each visit for all symptoms.

The time to response, defined as the time from the first injection to the first evaluation in which a patient reaches a tumor volume decrease of at least  $\geq 20\%$ , will be listed for all patients. If a patient did not reach tumor response, the period of his/her last evaluation will be used as a cutoff period. For responsive patients, average time to response will be summarized.

Additionally, logistic and cox regression models may be used to explore the association between baseline characteristics and tumor response and time to tumor response. These analyses will be specified in the report analysis plan (RAP).

The frequency and percentage of patients experiencing improvement of symptoms related to tumor compression, pituitary hormone dysfunction, normalization of the alpha subunit level, will be presented for each symptom at each period with the associated exact 90% CI.

The incidence rates of pituitary hormone dysfunction, the normalization of alpha subunit levels, and the proportion of patients with a 50% decrease in the alpha subunit level, together with the exact 90% CI will be reported at baseline and on weeks 4, 12, and 24. The alpha subunit level analyses will be performed again with the population set according to protocol and for the subgroup of patients with increased alpha subunit levels at baseline.

Hormone profiles, alpha subunit levels, in each period in terms of frequency (N), mean, standard deviation, median, minimum, and maximum.

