Hypopituitarism may occur in pituitary macroadenomas as a result of (a) compression of the pituitary stalk, leading to a decrease of hypothalamic hormones reaching the pituitary gland; (b) compression of the normal pituitary tissue; and (3) hypothalamic involvement of the pituitary tumor (Dekkers et al 2008). The hypogonadism seen with these adenomas is frequently associated to the increase in blood prolactin levels (usually < 200 ng/mL) (Jaffe 2006). Patients with hypopituitarism are at increased risk of mortality due to cardiovascular, cerebrovascular, and/or respiratory disease (Bates et al. 1996)(Rosen et al. 1990)(Bulow et al 1997)(Nilsson et al 2000)(Tomlinson et al 2001).

Hypopituitarism due to NFPA may produce different symptoms. Four out of five patients with NFPA experience secondary hypothyroidism, and 3 out of 5 experience secondary adrenal failure (Jaffe 2006). Most patients also experience signs and symptoms of hypogonadism, frequently as a result of direct compression by a large adenoma and growth hormone (GH) deficiency (Jaffe 2006). Approximately 60% to 80% of patients experience visual field defects, a consequence of tumor pressure on the optic chiasm (Jaffe 2006)(Dekkers et al 2007). In some cases, these tumors compress other surrounding brain tissues and lead to dysfunctions in the cranial nerves (Jaffe 2006)(Vance 2008). Frequently, patients experience headache, although this event is not diagnosed (Vance 2008).

The evaluation of the tumor volume and location of the pituitary adenoma are performed more efficiently by magnetic resonance imaging (MRI) (Dekkers et al 2008). Screening hormone tests that may determine pituitary deficiency include ACTH, cortisol, TSH, free thyroxin (T4), insulin-like growth factor I (IGF-1), luteinizing hormone (LH), follicle-stimulating hormone (FSH), and testosterone (in men) (Vance 2008). Prolactin is also useful for diagnosis, but it must be diluted if the patient presents a large lesion, in order to avoid the "hook effect" and a possible mistaken diagnosis (Vance 2008) (the hook effect may be defined as falsely low values in an immunoassay when an extremely large amount of antigens affects the binding ability of the antibody added).

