Merola et al 1993	19	0.15 - 0.3 mg/day SC	1-12	Decreased: 5% Unchanged: 95%	9 evaluable patients Improved: 11% Unchanged: 89%
Gasperi et al 1993	8	0.3 mg/day SC	3-6	Decreased: 0% Unchanged: 75% Increased: 25%	5 evaluable patients Improved: 20% Unchanged: 60% Worsened: 20%
de Bruin et al 1992	4	1.2 mg/day SC	3-6	Unchanged: 100%	Improved: 75% Unchanged: 25%

Combination therapy with dopamine receptor agonist cabergoline and somatostatin analogue octreotide in 10 patients with NFPA produced similar results (Andersen et al 2001). Tumor volume decreased in 6 patients (60%), remained unchanged in 3 (30%), and increased in 1 (10%) patient. Visual acuity improved in 3 (30%) patients and remained unchanged in the other 7 (70%) patients.

A clinical therapy able to control tumor growth and possibly capable of decreasing tumor size would be highly advantageous to patients with NFPA. These therapies could be used presurgically to improve surgical result, leading to few patients with remaining tumors, or to control tumor growth or recurrence after surgery, thus avoiding the need for radiation therapy. Another possible benefit related to tumor decrease would be the receovery from hypopituitarism.

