Padova et al. showed that SSTR2 and SSTR5 selective analogues decreased cell viability in 8/13 and 10/13 of NFPAs exposed to these in vitro peptides, respectively. This inhibitory effect of a compound tested for the number of viable cells in an adenoma culture reflects a probable antitumoral effect of this peptide (Colao et al 2008)(Padova et al 2008).

Pasireotide LAR (SOM230) is a new somatostatin analogue with properties similar to natural somatostatin and, specifically, high affinity and functional activity to sst 1, sst 2, sst 3, and sst 5 (Bruns et al 2002)(Schmid et al 2004). Pasireotide has been shown to inhibit GH and prolactin secretion from in vitro pituitary adenomas (Hofland et al 2004)(Murray et al 2004), in vitro ACTH, (Batista et al 2006), and in vivo GH/IGF-1 (Weckbecker et al 2002)(Fedele et al 2007). Additionally, pasireotide inhibited the proliferation of cells stimulated by endothelial VEGF (Adams et al 2004).

A pre-clinical trial showed that pasireotide avoids NFPA cell viability by inhibiting VEGF secretion, which indicates that this multireceptor SSTR agonist may be useful as medical therapy for NFPA (Zatelli et al 2007).

Pasireotide LAR was tested in clinical trials in healthy volunteers [CSOM230C2101] and in 2 populations of patients (i.e., acromegaly and carcinoid disease [CSOM230C2110]). However, there are no previous reports about the clinical use of pasireotide LAR for NFPAs.

Based on these findings and on the need of a medical therapy that may be used pre-surgically to improve surgical results, leading to less patients with remaining tumors, or to control tumor growth or recurrence after surgery, avoiding the need for radiation therapy, pasireotide LAR may be a good medical option for treatment, both as pre-surgical therapy and in the control of post-surgical tumor growth.

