#### 3.2.1 Secondary objective endpoints

The secondary variables are:

- Mean change in tumor volume evaluated by pituitary MRI between baseline and weeks 4, 12, 24, 48, 72, and 96.
- Percent change in tumor volume evaluated by pituitary MRI between baseline and weeks 4, 12, 24, 48, 72, and 96.
- Proportion of patients reaching tumor volume decrease of at least  $\geq$  20% after 4, 12, 48, 72, and 96 weeks of treatment.

- Time to treatment response for treatment responders, defined as the time from the date of the first injection to the first evaluation in which the patient reached a tumor volume decrease of at least ≥ 20%.
- Change in grading score of disease-related symptoms between baseline and weeks 4, 12, 24, 48, 72, and 96.
- Incidence of pituitary hormone dysfunction at baseline and on weeks 4, 12, 24, 48, 72, and 96.
- Proportion of patients reaching alpha subunit decrease of at least 50% on weeks 4, 12, 24, 48, 72, and 96.
- Proportion of patients reaching alpha subunit normalization on weeks 4, 12, 24, 48, 72, and 96.
- Percentage of adverse events with CTC grade  $\geq 3$  during treatment with pasireotide LAR.
- Percentage of patients with at least one adverse event with CTC grade  $\geq 3$ .
- Incidence of all adverse events, incidence of abnormal lab values, and summary of laboratory evaluations.
- For the extension phase: among patients who had been considered as responders (i.e., patients reaching a tumor volume decrease of at least 20% compared to initial tumor volume), to evaluate the number and proportion of patients who remained responsive during the extension phase treatment (according to the magnetic resonance imaging evaluations on weeks 48, 72, and 96).
- To evaluate the percentage of patients remaining with stable tumor volume during the study, i.e., patients who mantained tumor volume variation lower than 20% compared to baseline tumor volume (according to magnetic resonance imaging evaluations on weeks 24, 48, 72, and 96).
- If applicable, to evaluate whether there was a difference in response among patients on 40 and 60 mg doses of pasireotide LAR.

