5.5.1 Efficacy variables and analysis

The secondary efficacy endpoints are described in section 1.2.1.

The mean and percent change in tumor volume from baseline to Week 4, 12 and 24 will be presented along with the 90% confidence interval (CI). If data is found to be skewed, CIs for median will also be generated. Incidence rates for patients with \geq 20% reduction in tumor volume and its exact CI will be reported at Week 4 and 12.

Summary statistics will be provided for each disease related symptoms (headaches, visual disturbance, fatigue, symptoms specific to man and woman) at each visits. Change from baseline scores will be also summarized at each visit for all symptoms.

Time to response, defined as time from the first injection to first evaluation where patient achieve tumor volume reduction of at least \geq 20%, will be listed for all patients. If a patient has not achieved tumor response, the time of last assessment will be indicated as censoring time.

Kaplan-Meier analysis will be performed for time to response aiming to compute the median time to response and corresponding 95% confidence interval. Cox regression exploratory analysis will be used to estimate the hazard ratio with corresponding 95% confidence intervals for time to tumor volume reduction of at least \geq 20% as a function of baseline characteristics (duration of disease, dose at V2, dose reduction, visual field (abnormal/normal), and α subunit at V1).

Logistic regression will be performed to explore association between baseline characteristics and tumor response.

Frequency and percentage of patients who present improvement of symptoms related to tumor compression, pituitary hormonal dysfunction, alpha subunit level normalization, will be presented for each symptom at each time point with associated exact 95% CI.

Incidence rates of pituitary hormonal dysfunction, normalization of alpha subunit level and proportion of patients with 50% reduction in alpha subunit level along with its exact 95% CI will be reported at baseline, Week 4, 12 and 24. Analyses for alpha subunit level will be repeated with per protocol population set and for the subgroup of patients with elevated alpha subunit level at baseline.

Hormone profiles, alpha subunit levels and will be summarized at each time point in terms of frequency (N), mean, standard-deviation, median, minimum, and maximum.

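### The incidence of pituitary hormone dysfunction is a visit-wise prevalence with no at-risk denominator, so by itself it cannot separate new deficiency from recovery.

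*Protocol*

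**What the plan says.** The endpoint in protocol 3.2.1 is "Incidence of pituitary hormone dysfunction at baseline and on weeks 4, 12, 24, 48, 72, and 96"; SAP 1.2.1 has the same endpoint. For the main phase, protocol 10.5.1 plans "The incidence rates of pituitary hormone dysfunction, the normalization of alpha subunit levels", which "will be reported at baseline and on weeks 4, 12, and 24" with an exact 90% interval. SAP 5.5.1 plans "Incidence rates of pituitary hormonal dysfunction, normalization of alpha subunit level and proportion of patients with 50% reduction in alpha subunit level" at the same times with an exact 95% interval; SAP section 7 declares the move from 90% to 95%. Neither document limits the denominator to patients without dysfunction at baseline, defines dysfunction, or says how a patient on replacement is classified.

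Four other provisions bear on the point:

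- **Improvement.** The sentence just before, in both documents, plans the number of patients with improvement at each time point with an exact interval. Its list includes pituitary hormone dysfunction, but the result is to be shown for each symptom.
- **Adverse events and laboratory values.** Protocol 10.5.3.1 and 10.5.3.2 and SAP 5.5.3.1 and 5.5.3.2 plan summaries of adverse events and laboratory values that are new or worse than baseline, a baseline-to-worst comparison by CTC grade (called shift tables in the SAP), and listings with out-of-range values flagged.
- **Table shells.** SAP Table 30 gives each hormone as normal or abnormal at V1, V4, V7 and V10. Table B 23 does the same for the extension. Table 31 compares hormone levels by replacement therapy at V1 only.
- **Entry.** Exclusion criterion 32 admits patients with confirmed hypothyroidism, hypoadrenalism or hypogonadism if they are on stable replacement.

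**The concern.** The objective is the effect of pasireotide LAR on pituitary function. An effect means that patients change state: some lose an axis, some regain one. A share of patients with dysfunction at each visit shows only the net result.

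The distinction matters in this population for two reasons. Deficiency before treatment is expected: protocol 1.1 states "Four out of five patients with NFPA experience secondary hypothyroidism, and 3 out of 5 experience secondary adrenal failure", and criterion 32 lets treated deficiency in. The protocol also gives grounds to look in both directions. On recovery, section 1.1 says "Another possible benefit related to tumor decrease would be the receovery from hypopituitarism". On suppression, section 2 says "Pasireotide has been shown to inhibit GH and prolactin secretion from in vitro pituitary adenomas", and also cites inhibition of ACTH in vitro and of GH/IGF-1 in vivo. If both occur, a flat series could hide them. New adrenal or thyroid deficiency would also be of safety interest.

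The label adds a smaller problem: a reader who takes incidence at its usual meaning would credit to the treatment period cases that were present before the first injection.

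**Working it through.** **No figure to reproduce for this endpoint.** The documents state none. As a check of the interval method, exact (Clopper-Pearson) 90% limits reproduce protocol Table 10.2: 2/19 gives 1.9% to 29.6%, and 6/19 gives 14.7% to 53.0%.

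**Inputs.** N = 19 evaluable patients (protocol 10.6). Baseline cases B = 11 are assumed for illustration: 11/19 = 57.9%, near the 3 in 5 that protocol 1.1 quotes for adrenal failure. Data are assumed complete, with a fixed definition of dysfunction.

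**Identities.**

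- Cases at visit t = B + new − recovered.
- Planned figure at t = (B + new − recovered) / N.
- New onset = new / (N − B); here N − B = 19 − 11 = 8.
- Recovery = recovered / B; here B = 11.

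**Result when the planned figure does not move (new = recovered).** Week 24 is again 11/19 = 57.9%, with exact 90% limits 36.8% to 77.0% in every row:

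| New | Recovered | Week 24 | New onset | Exact 90% CI | Exact 95% CI | Recovery |
|---|---|---|---|---|---|---|
| 0 | 0 | 11/19 | 0/8 = 0% | 0% to 31.2% | 0% to 36.9% | 0/11 = 0% |
| 2 | 2 | 11/19 | 2/8 = 25% | 4.6% to 60.0% | 3.2% to 65.1% | 2/11 = 18.2% |
| 4 | 4 | 11/19 | 4/8 = 50% | 19.3% to 80.7% | 15.7% to 84.3% | 4/11 = 36.4% |
| 8 | 8 | 11/19 | 8/8 = 100% | 68.8% to 100% | 63.1% to 100% | 8/11 = 72.7% |

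**Dependence on the assumed baseline.** The number of offsetting changes cannot exceed min(B, N − B).

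- B = 4: a flat 4/19 (21.1%) fits 0/15 to 4/15 new cases, i.e. 0% to 26.7%.
- B = 15: a flat 15/19 (78.9%) fits 0/4 to 4/4.

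The ambiguity narrows when baseline dysfunction is rare, but does not vanish.

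**Can the planned improvement count resolve it?** Rearranging, new = (cases at t − B) + recovered. This works only if improvement means full recovery of function, the same patients are seen at both visits, and the count is produced for hormones. SAP 5.4.3 uses observed data, so visit denominators can differ. The definitions of improvement under SAP Table 10 concern symptoms only. No hormone shell carries the count.

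**The case against.** The strongest reply is that the information is not lost. Improvement is to be counted in the same section, and with complete data new cases follow by subtraction. A new deficiency that causes signs or symptoms, is clinically significant or requires therapy is an adverse event under protocol 7.5.1 and enters the treatment-emergent tables. Hormones are laboratory values, and with about 19 to 23 patients a flagged listing shows each new abnormality individually. These documents also use incidence rate loosely for any proportion, tumour response included, and the baseline figure stands beside the later ones. The endpoint is a descriptive secondary one in a proof-of-concept study.

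Much of this stands, and it rules out several stronger readings that a reader might infer:

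- *New deficiency is never shown.* Too absolute, given the adverse event tables and the listings.
- *Recovery is ignored.* It is planned, though ambiguously.
- *All axes are pooled into one rate.* Neither document says so, and Table 30 lists hormones separately.
- *Every patient deficient at entry is counted again at each visit.* This depends on the missing definition. If dysfunction means an out-of-range value, a replaced patient with normal free T4 may not count; if it means a diagnosis or replacement, the patient counts throughout.
- *Changes in GH/IGF-1 or ACTH reflect the drug and not the tumour.* Protocol section 2 gives laboratory and other in vivo findings, not data in these patients, and a single-arm study cannot separate the two.

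What the reply does not supply is a planned output. Adverse event reporting is selective for laboratory findings. The shift tables rest on CTC grades, the documents do not say hormones are graded, and the SAP has no shift-table shell. Tables 30 and B 23 do not cross-classify a visit against baseline.

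**Conclusion.** The concern holds in a limited form. The planned figure is a prevalence with no at-risk denominator, and by itself it cannot identify new onset: in the 19-patient illustration an unchanged 57.9% is compatible with 0% to 100% new dysfunction among the 8 at risk. New-onset deficiency is not part of the planned hormone analysis and would surface only indirectly.

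The size is illustrative. It rests on an assumed baseline count, complete data and a stable definition. The 4-in-5 and 3-in-5 figures describe single axes in NFPA generally, not this trial's entrants, so no forecast of baseline dysfunction or of the error follows from the documents. The primary endpoint is untouched. The change is worth making because the secondary endpoint as planned does not answer its own objective and the remedy is cheap.

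**What to change.** In protocol 10.5.1 and SAP 5.5.1:

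1. Relabel the visit rates as prevalence of pituitary hormone dysfunction.
2. State, per axis (thyroid, adrenal, gonadal, GH/IGF-1, prolactin), what counts as dysfunction and how patients on replacement are classified. The counts in step 3 cannot be programmed without this.
3. Add to the SAP a per-axis baseline-by-visit table at Weeks 4, 12 and 24. It should give new dysfunction among patients without it at baseline and recovery among patients with it, each with its own denominator and exact interval at the SAP's 95% level.
4. Show the GH/IGF-1 and ACTH/cortisol axes separately, without attributing changes there to drug rather than tumour.

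The cost is SAP wording and some table rows. Hormones are already measured at screening and at Weeks 4, 12 and 24 (protocol 7.4.2), so no new assessment is needed. The downside is small per-axis denominators and wide intervals: in the example, 2/8 new cases has a 95% interval of 3.2% to 65.1%.
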